1. SYNOPSIS

Study Title:	Vitamin D Levels in Subjects with Vitamin D Deficiency Following Topical Application of Vitamin D Gel – A Proof of Concept Study
Protocol Number:	VITD-001
Development Phase:	Phase 1
Indication:	Subjects with known vitamin D deficiency (<20 µg/L Total 25-OH Vitamin D)
Study Drugs: (Including test, comparator, dosage form, dosing regimen and route)	
A novel vitamin D₃ (cholecalciferol) is provided as a topical gel using ingredients that are identified in the USP/NF and/or designated in the list of Inactive Ingredients in FDA Approved Drugs. The ingredients in the topical gel are well known in the industry and have references in the pharmaceutical literature and some have available FDA drug master file information. A single applicator contains 0.75g of gel, containing 150,000 international units of vitamin D3 (cholecalciferol) to be applied to the upper arm. One dose consists of two applicators, one applied to each upper arm, for a total of 300,000 international units per dose.
 
Subjects with known vitamin D deficiency of ≤20 ng/ml total 25-OH Vitamin D (50 nmol/liter) will be consented and enrolled. They will have a blood draw prior to dosing on Day 1 (to obtain a baseline vitamin D, calcium, albumin, and parathyroid hormone level) and will receive 300,000 units of topical vitamin D3. On Day 7, subjects will return to the clinic for a blood draw to assess Vitamin D level and to check for any signs of skin rash and/or reaction. If a subject has a skin rash and/or reaction prior to Day 7, he/she will be advised to return to the clinic for assessment as soon as possible. Any rash and/or skin reaction may be photographed and diagnosed. A second dose of 300,000 units of topical Vitamin D will be applied by the nurse at the day 7 visit. Subjects will return on Day 14 for a third dose and a third blood draw. A final blood draw to assess for Vitamin D level will be done on day 21.
 
A study nurse or physician will apply each dose of topical Vitamin D. Prior to application of the gel, 2 strips of paper tape will be applied to the subject's upper arms. One strip will be applied approximately 2 inches below the subject's shoulder and the second strip will be applied approximately 2 inches above the subject's elbow. The entire contents of one syringe (0.25 mL of gel) will be applied onto the subjects arm in a straight line, from approximately 1 inch below the first strip of paper tape to approximately 1 inch above the second strip of paper tape. The subject will be instructed to gently rub the gel into their upper arm with their fingertips, while staying between the two pieces of paper tape, for approximately 2 minutes or until the gel has been absorbed. After completing the application process on both arms, the subject will wash his/her hands thoroughly.


No. Subjects:	20 subjects will participate. If the change from baseline in 25-OH vitamin D is consistently less than 10 µg/L in the first 10 subjects then the study will be discontinued.
No. Centers:	The study will be conducted at the University of Minnesota (single center)
Study Duration:	The maximum duration of treatment is 14 days (study Days 0, 7 and 14). Subjects will be followed for change in vitamin D blood level and for safety until Study Day 21. It is anticipated that the study will last 4 months to enroll and complete dosing and assessment of 20 patients.
Objectives of the Study:	The primary objective of the study is to determine the change in vitamin D blood levels following 3 doses of topical vitamin D ₃ treatment. The secondary objective is to assess the safety (based on skin rash and/or other reaction, as well as calcium and parathyroid hormone levels) following the application of 3 doses of vitamin D ₃ gel.
Study Endpoints: (Primary and Secondary)	The primary endpoint is to establish the average change in vitamin D blood levels following 3 doses of treatment with vitamin D gel. The secondary study endpoint is the number of subjects who have any skin rash and/or other skin reaction following treatment with the vitamin D gel.
Study Design:	The study is a pre vs. post open-label trial to assess the change in vitamin D blood levels following treatment with 3 doses of topical vitamin D gel. Subjects with known vitamin D deficiency will be consented and enrolled. They will have a blood draw prior to dosing on Day 0 (to obtain a baseline vitamin D level) and will receive topical vitamin D ₃ on Days 0, 7 and 14. On Days 7, 14, and 21 subjects will return to the clinic for a post-dose blood draw and to be assessed for any signs of skin rash and/or reaction. If a subject has a skin rash and/or reaction at any time during the study, he/she should return to the clinic for assessment as soon as possible. Any rash and/or skin reaction will be photographed and diagnosed.
Eligibility Criteria (Inclusion and Exclusion):	
Inclusion criteria:
 
 Known vitamin D deficiency based on blood work obtained prior to study consent defined as serum 25-hydroxyvitamin D less than or equal to 20 ng/mL within 30 days prior to study entry. (Normal \geq to 30 µg/L total 25-OH Vitamin D) Adult, age 18 to 85 years, male or female If on oral vitamin D therapy, have been on a stable dose for the previous 90 days.

Eligibility Criteria (continued):	
Exclusion criteria:
 
1. History of chronic liver disease with elevated liver function tests, chronic kidney disease (stage 3 or greater, eGFR <60 mL/min), uncontrolled thyroid disease (elevated thyroid function tests), primary or secondary hyperparathyroidism, hypercalcemia, or multiple endocrine neoplasia.2. Hypercalcemia defined as either elevated corrected serum calcium >10.2 mg/dL) measured within 3 months prior to study.3. eGFR <60 mL/min within 3 months prior to study.4. Active cancers5. Women who are pregnant or breastfeeding.6. Individuals who are unable to give informed consent7. Individuals with psoriasis, active eczema or other skin disease, or who are currently receiving treatments or medications for skin disease.8. Individuals who do not agree to refrain from using tanning beds for the duration of the study.9. Individuals who do not agree to avoid submerging the gel site in water for 8 hours after gel application.10. Family members of the study faculty or staff.
--	--

Study Procedures: (Including pharmacokinetic (PK) sampling times)
	
The following procedures will be performed during this study:
 
 • Chart review to assess for potential eligibility • Day 0 
 ○ Subject informed consent ○ Measurement of height and weight and examination of skin for rash/appearance to confirm eligibility ○ Record Fitzpatrick skin test score. ○ Blood draw for baseline vitamin D levels (total vitamin D 25-OH and vitamin D3) ○ Blood draw for serum creatinine (for GFR calculation), albumin (for corrected calcium) and parathyroid hormone ○ Application of Vitamin D gel by study staff to inside of each arm ○ Instruct subject on assessment of skin. If any rash or other skin reaction appears, contact the clinic as soon as possible for an assessment. • Day 7 
 ○ Assessment of skin for rash or other reaction ○ Draw blood for Ca, vitamin D level. ○ Application of Vitamin D gel by study staff to inside of each arm. • Day 14 
 ○ Assessment of skin for rash or other reaction ○ Draw blood for Ca, vitamin D level. ○ Application of Vitamin D gel by study staff to inside of each arm. • Day 21 
 ○ Assessment of skin for rash or other reaction ○ Blood draw for post dose vitamin D, calcium, and parathyroid hormone level.

Safety
	
All subjects will be monitored for skin rash or other reactions. Any rash and/or reaction will be photographed by study staff and assessed/diagnosed by a physician.
 
Patient will have serum calcium followed each week during the study. Although it is unlikely that calcium will change with an increase in topical Vitamin D, hypercalcemia presents a potential theoretic risk if absorption is high or unexpected variability in vitamin D absorption exists.

Laboratory Parameters/Analysis:
	
Laboratory analyses will consist of 25-hydroxyvitamin D blood levels (D2 and D3) and parathyroid hormone levels. For safety, an albumen adjusted calcium determination will be measured on day 0, 7, 14, and 21.

Total Blood Volume:
	
Approximately 5 mL will be required at day 0, 7, 14, and 21 to assess for vitamin D parameters and safety.

Sample Size Determination: (If applicable)	The study will have 20 subjects who are evaluable for changes in vitamin D blood levels.
Statistical Analyses: (Brief Description)	Two sample paired t test of pre and post total vitamin D and parathyroid hormone with an alpha of .05. We do not expect any significant change in adjusted calcium.

2. STUDY SCHEDULE

Table 1: Schedule of Events

Clinical/Study Assessment	Prescreening	Testing Visits			
		Day 0	Day 7	Day 14	Day 21
Chart review for potential eligibility	X				
Physical Exam of skin* · Skin integrity assessment · Fitzpatrick skin score		X**	X**	X**	X**
Blood Draw: · Serum 25-OH vitamin D · Serum calcium		X	X	X	X
· Serum creatinine (eGFR) · Serum albumin		X			
· Serum parathyroid hormone		X			X
Topical Treatment Application		X	X	X	

* Subjects will be instructed to contact the site as soon as possible if he/she notices a skin rash or any other reaction.

**A digital photograph may be taken to record any signs of irritation or reaction.

3.	TABLE OF CONTENTS	
1.	TITLE PAGEError! Bookmark not defined.
2.	SYNOPSIS2
3.	STUDY SCHEDULE7
4.	TABLE OF CONTENTS8
5.	LIST OF ABBREVIATIONS AND DEFINITIONS OF TERMS11
6.	INTRODUCTION12

4. LIST OF ABBREVIATIONS AND DEFINITIONS OF TERMS

Abbreviation	Definition
µg	Microgram(s)
AE	Adverse event
CRF	Case report form
g	Gram(s)
GCP	Good Clinical Practice
ICF	Informed Consent Form
ICH	International Conference on Harmonisation
IND	Investigational New Drug
IRB	Institutional Review Board
kg	Kilogram(s)
L	Liter
MedDRA	Medical Dictionary for Regulatory Activities
mg	Milligram(s)
mL	Milliliter
SAE	Serious adverse event

5. INTRODUCTION

5.1 Vitamin D Deficiency

Vitamin D insufficiency is an emerging and compelling public health issue. Recent studies suggest that 19% of the U.S. population is at risk for vitamin D inadequacy¹, although this may underestimate the number of people at risk from suboptimal vitamin D levels². More than 40% of U.S. and European elderly men and women living in the community are deficient in Vitamin D³, and more than 50% of postmenopausal women taking medication for osteoporosis⁴. Diverse population subgroups are deficient in Vitamin D including Arab women and lactose intolerant individuals who consume less vitamin D from fortified products⁵. In a Boston hospital, 25% of healthy students, physicians, and residents were found to be vitamin D-deficient, despite drinking a glass of milk and taking a multivitamin daily and eating salmon at least once a week⁶. By the end of the winter, it has been estimated that 42% of 15- to 49-year-old black females throughout the United States have 25-hydroxyvitamin D levels below 20 ng per milliliter. The implications of this are far-reaching. In addition to well-known impacts on bone health, vitamin D status is thought to potentially influence a number of common diseases, including cancers, autoimmune disorders, and cardiovascular disease. Vitamin D deficiency may increase the risk of injury from falls as people age⁷, while early in life Vitamin D deficiency has been associated with increased risk of Type 1 diabetes^{8,9}. Other patient populations at increased risk for vitamin D insufficiency include individuals with fat malabsorption, chronic kidney disease, or obesity^{10,11,12}.

The Endocrine Society defines vitamin D deficiency as a 25(OH)D of 20 ng/ml (50 nmol/liter) or below, and vitamin D insufficiency as a 25(OH)D of 21–29 ng/ml (525–725 nmol/liter)¹³. They recommend measuring vitamin D using the serum circulating 25-hydroxyvitamin D (25(OH)D). The Institute of Medicine reports that persons are potentially at risk for inadequacy at serum 25OHD levels between 12 and 20 ng/mL (30 and 50 nmol/L)¹⁴. In sun-rich environments, normal levels have been estimated to be 54-90 ng/ml¹⁵. Although it is not known what the safe upper value for 25(OH)D is for avoiding hypercalcemia, most studies in children and adults have suggested that the blood levels need to be above 150 ng/ml before any concern arises¹⁶.

Of all of the forms of vitamin D, cholecalciferol (Vitamin D3) has been viewed as having the best overall combination of safety and efficacy, assuming normal kidney and liver function. In the US, cholecalciferol has primarily been available as an oral supplement at fairly low doses (most commonly 1000 – 2000 IU). In otherwise healthy patients, a common US standard of care for treatment of low serum vitamin D is to give 50,000 IU Vitamin D orally per week for four weeks (total dose 200,000 IU) until levels are brought up into the adequate

[figure not shown]

Figure 1. Absorption kinetics of oral Vitamin D3.

effective long term treatment of vitamin D deficiency. The proposed study aims to investigate both safety and efficacy of a topically applied vitamin D that is likely to be more effective, convenient, or acceptable for many individuals.

A wide variety of dosing schedules for Vitamin D have been documented¹⁸. Recently Vieth's team conducted a study with oral cholecalciferol in 48 elderly women (81 ± 8 years)¹⁹. The study tested oral cholecalciferol (D3) up to 45,000 IU once every 28 days. The study showed that a single oral dose of 45,000 IU dissolved in alcohol generally produced a rise in serum vitamin D of about 10 ng/ml. A second oral dose 28 days later further increased the serum vitamin D level by about another 10 ng/ml. Thus, the total increase after two oral doses (90,000 IU) was about 20 ng/ml. Although following oral dosing, rises in serum Vit D can be seen up to one month following administration, Vieth's study demonstrated that most of the rise (>60%) in Vitamin D occurs within 7 days. (Figure 1). No one receiving oral monthly dosing of 45,000 IU Vitamin D3 developed hypercalcemia.

Vitamin D Product Development

Innovative Pharmacy Services, Inc. has developed a vitamin D3 topical gel using ingredients that are identified in the USP/NF and/or designated in the list of Inactive Ingredients in FDA Approved Drugs. The ingredients in the topical gel are well known in the industry and have references in the pharmaceutical literature and some have available FDA drug master file information. A single applicator contains 0.75 g of gel, containing 150,000 international units of vitamin D3 (cholecalciferol). One dose will consist of two applicators. One applicator will be applied to each of the subject's upper arm for a total dose of 300,000 units.

range, followed by daily supplements of 2,000 IU. This is often provided as commercially available Vitamin D2, however supplementation with Vitamin D3 appears to be more potent and may provide other benefits¹⁷.

Despite the widespread availability of oral supplementation, the frequency of vitamin D deficiency remains high. Some individuals have difficulty taking pills, while others, especially the elderly, may be overwhelmed by their number of oral medications. A need exists for a more convenient delivery mechanism that enhance access to

5.2 Study Rationale and Selection of Dose

5.2.1 Rationale for Study

The purpose of this investigation is to demonstrate that a novel topical vitamin D3 (cholecalciferol) gel is bioavailable to the systemic circulation and in sufficient quantities to treat hypovitaminosis D. In Phase Ia, healthy volunteers will be dosed with a topical gel to determine increases of serum 25-OH vitamin D that can be expected from three doses. The application will take place in the winter months in Minnesota. Although ambient levels of light are low at that time, subjects will be asked to avoid attending tanning booths, and to wear a comfortable shirt that covers their upper arms at least to the elbow if they choose to go outside during daylight hours.

5.2.2 Rationale for Selected Dose

A wide variation in Vitamin D dosing has been used in clinical practice¹². If we assume that the topical gel vitamin D dosing has no greater bioavailability than intramuscularly injected dosing, then the maximal effect of 100,000 IU of Vitamin D3 applied topically would be expected to reflect that of a single 100,000 IU injected dose¹⁹. The supplementation protocol most often used in France to correct vitamin D levels of ≥ 10 ng/ml and <20 ng/ml is three doses of 100,000 IU of Vitamin D3 given intramuscularly one week apart²⁰. For values ≤ 10 ng/ml four doses of 100,000 IU are administered. An observational study of this common French protocol by Rouillon evaluated 204 patients receiving 3-4 doses of 100,000 IU Vitamin D3 weekly for vitamin deficiency (Groups 1 and 2)²¹. Rouillon found the protocol to be safe with no episodes of hypercalcemia. Two patients from the total of 257 studied developed Vitamin D levels over 90 ng/ml (one 92 mg/ml and one 94 ng/ml), with both resolving within one month. .

The proposed study will use a topical application of Vitamin D which is unlikely to be as completely absorbed as intramuscular injection. Furthermore, topical application of Vitamin D provides important additional physiologic mechanisms that reduce the potential for possible hypervitaminosis. Upon exposure to UVB radiation, previtamin D3 is synthesized from 7-DHC in the stratum basale and stratum spinosum layers of the epidermis. Previtamin D3 thermoisomerizes to vitamin D3 with heat or sunlight exposure at the ultraviolet region of the solar spectrum around 316-330 nm²². Vitamin D3 is then available for binding with a vitamin D binding protein (DBP) and transported into the circulation²³. In the skin, the DBP acts as a regulatory mechanism preventing over absorption of Vitamin D into the circulation by providing a threshold when the binding protein has been fully occupied. Upon exposure to sunlight, vitamin D3 itself is rapidly degraded to other photoproducts, including 5,6-trans-vitamin D3, suprasterol I, and suprasterol II²⁴. Although winter sunlight is not strong enough to produce vitamin D3 in the skin, it is strong enough to promote the photodestruction of existing vitamin D²⁴. Neither binding with DBP nor other serum components prevent photodestruction.).

In the process of normal physiologic production, previtamin D3 can isomerize in a reversible reaction to form the photoproducts, tachysterol-3 or lumisterol-3. These isomers do not enhance intestinal calcium absorption and do not significantly enter the circulation. The inactive metabolic products are sloughed off when skin cells are naturally shed. Removal of previtamin D3 provides a mechanism to prevent vitamin D toxicity from prolonged sun

exposure²⁵, and may further increase the potential safety of topical Vitamin D3 administration. The Mayo Clinic reports that Vitamin D is 'likely' safe when applied to the skin¹².

The effectiveness of topical absorption for the proposed product is unknown, however topical absorption is substantially less effective than the intramuscular injection of Vitamin D3. In the first three candidates, 300,000 units applied over three weeks resulted in an insignificant average change in Vitamin D level, as follows.

Baseline	Week 1	Week 2	Week 3	change
10.2	9.4	10.4	12.1	1.2

Oral administration of 50,000 IU should produce a 10 ng/ml increase in total serum Vitamin D¹³. The topical application of 300,000 IU, therefore, was substantially less effective than one 50,000 IU oral dose. . The study will use three doses of 300,000 IU applied one week apart with safety and outcome measures after each. This is hoped to provide a greater difference in vitamin D level than that seen in one oral 50,000IU supplement, but should produce less change than the typical US replacement dosing of three oral supplements, If the change in total serum Vitamin D level after the topical application of 900,000 IU in the first 10 subjects is consistently less than 10 mg/ml then the study will be discontinued.

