8.4 Replacement of Subjects

Subjects who withdraw or are removed from the study prior having their Day 7 blood draw for a reason other than a drug-related adverse event will be replaced.

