14. DATA ANALYSIS AND STATISTICAL CONSIDERATIONS

Data for this study will be entered into a REDCap database, which uses a MySQL database via a secure web interface with data checks used during data entry to ensure data quality. REDCap includes a complete suite of features to support HIPAA compliance, including a full audit trail, user-based privileges, and integration with the institutional LDAP server. The MySQL database and the web server will both be housed on secure servers operated by the University of Minnesota Academic Health Center's Information Systems group (AHC-IS). The servers are in a physically secure location on campus and are backed up nightly, with the backups stored in accordance with the AHC-IS retention schedule of daily, weekly, and monthly tapes retained for 1 month, 3 months, and 6 months, respectively. Weekly backup tapes are stored offsite. The AHC-IS servers provide a stable, secure, well-maintained, and high-capacity data storage environment, and both REDCap and MySQL are widely-used, powerful, reliable, well-supported systems. Access to the study's data in REDCap will be restricted to the members of the study team by username and password.

The general analytical approach for all endpoints will be descriptive in nature. No formal statistical hypothesis testing will be conducted. No p-values will be presented due to the small sample size of this study. Data analyses will be provided for all study subjects combined wherever appropriate.

For continuous variables, summary statistics will include number of subjects, mean, median, standard deviation, minimum, and maximum. For categorical variables, descriptive statistics will include number of subjects and percentages.

In regards to handling of missing data, there will be no imputation of missing values.

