14.1 Analysis Populations

Safety Population: all subjects who receive at least 1 dose of study drug and who have at least one post-dosing safety evaluation. All safety endpoints, baseline characteristics, and demographic data will be summarized using the Safety Population.

Efficacy Evaluable Population: all subjects who receive all 3 doses of study drug and have a follow up blood draw for vitamin D levels, or discontinue prior to completing dosing due to a drug-related adverse event. Vitamin D level data will be analyzed using the Efficacy Evaluable Population.

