14.4 Determination of Sample Size

A change from baseline of 10 $\mu\text{g/L}$ in total 25-OH Vitamin D levels in subjects with Vitamin D deficiency is thought to be a clinically relevant improvement. Assuming that the standard deviation for pre and post measures of total 25-OH Vitamin D is 4 $\mu\text{g/L}$, then the standard deviation of the difference is 5.6 $\mu\text{g/L}$ so 10 subjects should be adequate to show an effect size of 6.4 $\mu\text{g/L}$ with alpha of .05 and a power of 90%. However the standard deviation of the second measure is unknown since absorption may vary by individual. Assuming the standard deviation of the second measure increases to 12, then 20 subjects would be needed to detect an effect size of 10 $\mu\text{g/L}$. In order to be most conservative, 20 subjects will be treated in this proof-of-concept study.

ETHICS

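### The first-10-subjects discontinuation rule prints its threshold in the wrong unit in Protocol 5.2.2, and neither statement of the rule gives *consistently* a count

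*Protocol*

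**What the plan says.** The rule appears twice in the Protocol.

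- **Synopsis, No. Subjects:** "If the change from baseline in 25-OH vitamin D is consistently less than 10" µg/L in the first 10 subjects, the study stops. No assessment day is given.
- **Section 5.2.2:** the change after 900,000 IU is the criterion, and if it "in the first 10 subjects is consistently less than 10 mg/ml then the study will be discontinued".

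Neither place says how many of the 10 subjects must fall below the threshold. The rule is not repeated in Protocol section 14, in section 15.8 on termination, or in the SAP.

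Three nearby statements bear on the unit. The paragraph of 5.2.2 that holds the rule sets its benchmark in ng/ml: "Oral administration of 50,000 IU should produce a 10 ng/ml increase in total serum Vitamin D". Section 14.4 (and SAP 1.4) says that a change of 10 µg/L "in total 25-OH Vitamin D levels in subjects with Vitamin D deficiency is thought to be a clinically relevant improvement". Earlier in 5.2.2 the same slip occurs within one phrase about two patients: "one 92 mg/ml and one 94 ng/ml".

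Section 14 and the SAP also state that "The general analytical approach for all endpoints will be descriptive in nature", with no hypothesis tests and no p-values.

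**The concern.** A wrong unit in background text is a copy-editing matter. Here it sits in a threshold on which someone must act, and as printed in 5.2.2 it could never fail to be met.

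The missing count matters more. All 10, 9 of 10 and 8 of 10 are each arguable meanings of *consistently*. The study is open-label, so the results of the first 10 subjects will be visible when the word is interpreted. The meaning could then be settled after the data are seen. Either further subjects would receive a weak gel, or the study would stop on a reading that nobody had fixed beforehand.

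**Working it through.** **Unit.** 10 mg/ml = 10,000,000 µg/L, and 10 ng/mL = 10 µg/L. The ratio is 10^6. The Synopsis, the 5.2.2 benchmark and section 14.4 all agree on 10 ng/mL (= 10 µg/L), so 5.2.2 contains a misprint.

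**SDs of the change, from section 14.4.**

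- Pre and post SD 4 each: √(4² + 4²) = 5.66, which the plan prints as 5.6. This implies zero pre/post correlation.
- Post SD 12: √(4² + 12²) = 12.65 by the same formula. The plan does not print this value.
- Sensitivity case, my assumption of correlation 0.5 with both SDs 4: √(16 + 16 − 2 × 0.5 × 16) = 4.0.

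**The plan's own figures.** For a paired t test at two-sided alpha 0.05 (sidedness is not stated, so this is assumed), 10 subjects with a change of 6.4 and SD 5.6 give 89.4% power, against the stated 90%. With a change of 10 and SD 12.65, 90% power needs 19 subjects, and 20 give 91.8%. Both stated sample sizes reproduce closely, which supports using these SDs. The plan gives no stopping probabilities for the rule.

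**Stopping probabilities.** Take the changes as independent and normal with mean m and standard deviation SD. Then p = Φ((10 − m)/SD) is the chance that one subject's change is below 10.

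- All 10: p^10
- At least 9: p^10 + 10p^9(1 − p)
- At least 8: the previous line + 45p^8(1 − p)²

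Worked case, m = 5 and SD 5.66: p = 0.8116. All 10 gives 0.124. At least 9 gives 0.124 + 0.288 = 0.412. At least 8 gives 0.412 + 0.301 = 0.713. A simulation of 400,000 trials returned 12.4% for all 10 and 71.2% for at least 8.

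| True change (µg/L) | SD | p | All 10 | ≥ 9 of 10 | ≥ 8 of 10 |
|---|---|---|---|---|---|
| 0 | 4.0 | 0.9938 | 94% | 99.8% | about 100% |
| 0 | 5.66 | 0.9615 | 67% | 95% | 99% |
| 0 | 12.65 | 0.7854 | 9% | 33% | 63% |
| 5 | 4.0 | 0.8944 | 33% | 71% | 92% |
| 5 | 5.66 | 0.8116 | 12% | 41% | 71% |
| 5 | 12.65 | 0.6537 | 1.4% | 9% | 27% |
| 10 | any | 0.5 | 0.1% | 1.1% | 5.5% |
| 15 | 12.65 | 0.3463 | about 0% | 0.05% | 0.5% |

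At a true change of 15 with SD 5.66, all three readings stop less than 0.01% of the time.

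The true change of 5 (halfway between no effect and the threshold) and the cut-offs of 9 and 8 are mine and are not in the documents. Section 14.4 links the larger SD to variable absorption, so 12.65 is less plausible for a gel that is not absorbed at all.

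**Dose the rule refers to.** 3 × 300,000 = 900,000 IU, as 5.2.2 says. Protocol 13.1.1, Protocol 14.3.5 and SAP 1.3.5 describe 100,000 IU weekly, which gives 3 × 100,000 = 300,000 IU. Under that text no subject would reach the total that the rule names.

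**The case against.** The strongest reply is that nobody would apply 10 mg/ml, that *consistently* in ordinary use means all or nearly all, and that section 15.8 lets the sponsor-investigator stop early for valid scientific reasons anyway. In a small, single-arm, descriptive study little then hangs on the wording. Much of this stands. However, section 15.8 gives a general right to stop and does not define the specific rule that the Protocol chose to state. All-or-nearly-all also still spans 12% to 41% in the worked case.

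A reader might infer four stronger points, which the documents do not support:

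- **Two competing thresholds.** The surrounding text shows one intended value and one misprint.
- **12% against 71% as a property of this trial.** The contrast depends on the chosen true change, cut-off and SD. The 71% belongs to the loosest of the three readings. At a true change of 10 or more the readings hardly differ.
- **The rule decides whether 10 or 20 subjects are treated.** No section pauses enrolment until the tenth subject reaches Day 21. The planned 4 months are about 17.4 weeks. Less 3 weeks of follow-up, and assuming uniform accrual, that is 20/14.4 ≈ 1.4 subjects per week, so about 4 more would be enrolled while that result is awaited.
- **The rule conflicts with the population definitions.** The Efficacy Evaluable Population does admit subjects who "or discontinue prior to completing dosing due to a drug-related adverse event", and section 8.4 limits replacement to those leaving before the Day 7 draw "for a reason other than a drug-related adverse event will be replaced". But the rule invokes neither section, and its 900,000 IU wording already points to subjects who received all three doses. What remains is that the Day 21 assessment is implied and not written.

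Absence from the SAP is weak evidence of a defect in itself, since the SAP largely reproduces section 14.

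**Conclusion.** The point holds in two parts. First, the threshold in 5.2.2 is wrong as printed, by a factor of a million, through a unit slip. Second, *consistently* is undefined, and this matters mainly for a gel with a weak effect. At a true change of 5 µg/L the three readings range from 12% to 71% (SD 5.66), 33% to 92% (SD 4.0) or 1.4% to 27% (SD 12.65). These figures assume normal, independent changes; SDs 5.66 and 12.65 also assume zero pre/post correlation, and SD 4.0 assumes 0.5.

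The practical weight is modest. A futility stop cannot produce a false efficacy claim, a general right to stop exists regardless, and some subjects beyond the tenth may already be enrolled when the rule is applied. It should be fixed because it is the only efficacy-based discontinuation rule in the plan and clarifying it costs almost nothing.

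**What to change.** 1. In 5.2.2, correct the unit of the threshold to ng/mL, matching the Synopsis.
2. In the Synopsis and 5.2.2, replace *consistently* with one count fixed in advance. Apply it to the Day 0 to Day 21 change in total 25-OH vitamin D, in the first 10 subjects who have all three doses of the reconciled regimen and a Day 21 value.
3. Repeat the rule in Protocol section 14 and the SAP, labelled as a decision rule and not a hypothesis test, so that it sits alongside the descriptive plan.
4. State the stopping probabilities of the chosen count in full. If at least 8 of 10 below 10 ng/mL were taken as an example, the figures for SD 4.0 / 5.66 / 12.65 are about 100% / 99% / 63% at zero effect and 92% / 71% / 27% at a true change of 5. They are 5.5% at a true change of 10 for any SD, and at most 0.5% at 15. The 63% should not be left out: under that SD an ineffective gel would continue about 37% of the time. Another count would serve equally well if it is fixed beforehand.
5. Separately, the sections giving 100,000 IU weekly (Protocol 13.1.1 and 14.3.5, SAP 1.3.5) contradict those giving 300,000 IU per dose (Synopsis, Protocol 5.2.2, 6 and 7.1). They must be reconciled, since the rule refers to 900,000 IU.

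For the rule itself, the cost is a sentence or so in each of four places, with no added subjects or visits. The sponsor gives up discretion over what *consistently* means, and the general right in section 15.8 is unaffected.
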